Injection of the ASCs or placebo-suspensions into submandibular glands will be performed by the principal investigator ([name]) under local anesthesia using ultrasonic guidance and sterile technique. The ASCs will be suspended in isotonic NaCl (0.9 mg/ml) and human albumin (HA) 1% to a final volume of 2 ml. Placebo will be 2 ml of isotonic NaCl (0.9 mg/ml) and HA 1%. After receiving the ASC-suspension or placebo-suspension, the surgeon (the principal investigator) will identify the submandibular glands and inject the ASC suspension. Calculation of injected number of ASCs pr. participant rests on the following calculation: $Suspension_{ml} = 2.8 \times 10^6 \frac{ASC}{cm^3} \times volume_{cm^3}$, where volume is the volume of the submandibular gland, and a gland-volume of approx. $7\text{-}8 \text{ cm}^3$ is the norm. Therefore, the amount of ASCs given to each participant will be approx. $2.8 \times 10^6 \frac{ASC}{cm^3} \times 8cm^3 \times 2 = 4.48 \times 10^6 \text{ ASCs}$ in total. If the expanded number of ASCs does not fulfil the above criteria, it is accepted to diminish the number to a minimum of 50% of the calculated dose.

Justification for patient population

In order to standardize the participant population, we choose to only include participants treated for a human papilloma virus (HPV)-positive oropharyngeal squamous cell carcinoma, and exclude patients with severe salivary gland hypofunction and already manifest or near-manifest xerostomia, as this population most likely will not benefit from this treatment. This will be assessed by a preliminary questionnaire and a subsequent saliva flow rate measurement before inclusion.

Eligibility criteria

Evaluation of eligibility criterias and consent forms are collected by the Primary Investigator.

Inclusion criteria:

- Previous radiotherapy for a T1-T2 and N0, N1 or N2a, HPV-positive oropharyngeal squamous cell carcinoma with bilateral irradiation of the neck
- 2 years follow-up without recurrence
- Clinically reduced salivation and hyposalivation, evaluated by a screening
 - Unstimulated whole saliva flow rate in the range of 0.05-0.20 ml/min
- Informed consent
- Grade 1-3 xerostomia as evaluated by the “Udvalg for Kliniske Undersøgelser” (UKU) side effect rating scale[26].

Exclusion criteria:

- Any cancer in the previous 2 years
- Ongoing xerogenic medications
- Any other diseases of the salivary glands, e.g. Sjögrens syndrome, sialolithiasis, etc.

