The procedure will be performed without local anesthesia in an outpatient setting. The surgeon will receive two syringes of the sterile ASC-suspension or placebo of each 1 ml (total of 2 ml). The suspensions are injected into each submandibular gland guided by ultrasound. The ASC-suspension will be deposited in two areas (superficial and deep lobe) with equal volume per site (0.5ml) to ensure equal distribution of the suspension. The subject will afterwards receive a small band aid,

which can be removed the same day. The participant will be administered over the counter pain relief.

Assessment of xerostomia and subjective treatment outcome

The subjective effect of the treatment is assessed by a 100 mm visual analogue scale of xerostomia filled out by the patient [27] and a physician-rated questionnaire [28], both carried out at baseline as well as one and four month after treatment (Figure 1).

Assessment of salivary flow rate and objective treatment outcome

Changes in the secretion rate of the unstimulated whole saliva in the oral cavity is probably the most important parameter for the biological development of xerostomia and accompanying pathological oral conditions. Whole saliva, e.g., the secretions from the major and minor salivary glands are mixed in the oral cavity. A precise determination of this value is crucial for the assessment of efficacy in this trial. For determination of the saliva flow rate, whole saliva will be collected between 2 p.m. and 3 p.m. for all collections to take the salivary diurnal variation into account. Participants will refrain from eating, drinking, smoking and oral hygiene for 2 hrs. prior to collection. After being seated upright in a chair, subjects relax for 5 min and are then instructed to make as few movements as possible, including swallowing, during the collection.

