At baseline, one and four months after treatment, unstimulated whole saliva will be collected using the spitting method [29] where participants spit their saliva into a collection container over a period of 15 minutes. The salivary flow rate (SFR) (ml/min) is determined as the increase in weight of the container divided by the collection time in minutes. After the collection of unstimulated saliva, the subjects are instructed to chew on 1 g of sterile paraffin wax. Participants will chew for 60 s, and clear the oral cavity for saliva. Subsequently, as the glands are now in a stimulated state, participants will continue chewing the paraffin wax and expectorate into a saliva collector for the duration of five minutes. Subsequently, testing of the submandibular glands will be performed. To assess ASC efficacy on the submandibular glands, saliva is also collected directly from the floor of the mouth in an unstimulated and stimulated state. The flow rate of the submandibular glands will be assessed by the swab method with cotton rolls placed buccally in each maxillary molar region to block the orifices of the parotid ducts and cotton rolls under the tongue in the floor of the mouth to collect submandibular/sublingual saliva. Immediately prior to the start of collection participants will be asked to swallow. Unstimulated saliva testing will be performed with neutral

cotton rolls(Salivette ®, Sarstedt, Nümbrecht, Germany) and stimulated saliva testing with cotton rolls with 20 mg citric acid (Salivette with citric acid ®, Sarstedt, Nümbrecht, Germany). For both measurements, collections takes place during a period of 3 min. Saliva flow rates are determined by weight (1 g equals 1 ml of saliva) with cotton rolls weighed before collection and reweighed after. The flow rates are calculated as the increase in weight during collection and expressed as millilitres per minute. Saliva from the cotton rolls will be extracted by centrifugation (1500 g) and analyzed for its composition. From each of these collections, saliva will be aliquoted and stored at -80°C.

Chemical analysis of saliva

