Whole saliva contains a large number of bacteria and epithelial cells, as well as gingival crevicular fluid. Therefore, whole saliva is normally not suited for the analysis of sensitive chemical parameters. For this purpose, non-contaminated selectively collected saliva from individual glands: i.e. parotid and submandibular/sublingual saliva is more suitable. The following analyzes will be performed on the collected saliva: pH and bicarbonate by ionic balance estimation [30], sodium, potassium, calcium, phosphate, chloride and fluoride [16], total protein, selected proteins [31] and amylase [32]. Chemical analysis will provide an estimate of dental and mucosal protective capacity of the saliva before and after treatment.

MRI analysis of the submandibular glands

A 3.0-Tesla 4-channel head coil and a dual-channel neck coil are employed to obtain hsMRI images of subjects (Siemens Magnetom Verio; Erlangen, Germany).

Volumetric and tissue-specific analysis will be performed based on axial and coronal sequences with 72 slices and 4-mm slice thickness including diffusion weighted and dynamic contrast-induced sequences. The contrast agent used is Gadolinium (“Gadovist”).

Statistical analyses

Data will be analyzed with SPSS v. 24 (IBM) or R statistics. We will use Excel or Access databases for collecting and entering data. All data will be double-entered. End of trial is defined as: last patient’s last visit (LPLV).

The results on salivary flow rate will be calculated as a percentage change in salivary flow rate (from baseline) in the group of participants given ASCs compared to the change-score in the control group.

Histologically, the composition of glandular tissue in the submandibular gland will be calculated

from before (baseline) and four months after the intervention (Figure 1). The differences between the intervention and the placebo group will be calculated by a non-paired t-test, alternatively a non-parametric test, if the conditions for parametric tests are not present. Differences are considered statistically significant if the two-sided p-value is less than 0.05.

Sample size calculation

The following sample size determination is based on a non-paired t-test. The minimal change in salivary flow rate that we want to be able to determine is 50%.

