Standard deviation (SD) of a salivary flow rate measurement can, using the spitting method in healthy participants and under completely standardized conditions, be minimized to about 20%. The SD can vary greatly and we have, therefore, in this test used a value from the published literature [33] for persons with reduced unstimulated whole salivary flow rate (from 0.00 to 0.20 ml/min) and/or hyposalivation (< 0.10 mL/min) indicating a relative SD of 58% of these groups. However, since we are interested in a comparison of change scores (change from baseline to after treatment) between the intervention and placebo group we apply the rule of thumb that the SD of the change score equals $SD/2^{0.5}$, which equals an SD of approximately 41%. The power is set at $(1-\beta)$: 90%. Significance level (α) is set at 0.05. This is a trial with a continuous response variable from independent control and experimental research unit with one control per experimental research unit. If the true difference in the change score between experimental and control means is 50%, we will need to study 15 participants for the experimental intervention and 15 patients as control population in order to reject the null hypothesis that the population means of the experimental and control groups are equal with a study power of 90%. The Type I error probability associated with this test of this null hypothesis is 0.05.

All investigators will have access to the final trial dataset.

Discussion

This first-in-man trial aims to establish the safety, efficacy and feasibility of autologous, adipose-derived stem cell therapy for patients with radiation-induced xerostomia. In addition, it provides an opportunity to advance trial methodology for the assessment of the putative role of stem cell therapy and provide suggestions for the design of subsequent trials to verify potential efficacy. To establish safety profile of the intervention, selection and timing of appropriate outcomes have been guided by similar intervention studies [34], and our trial design facilitates conditions for assessment

of short and long-term changes and complications.

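### Salivary flow, which sets the sample size, is compared as unadjusted percentage change with no visit named and its lead measure only implied; fix one baseline-adjusted comparison before unblinding

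*Combined protocol and SAP*

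**What the plan says.** All references are to the combined protocol and SAP.

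- **Outcome scale** (Statistical analyses): "results on salivary flow rate will be calculated as a percentage change in salivary flow rate (from baseline") in the ASC arm, set against the control arm's change score. No covariate or model is named.
- **Test** (same section, directly after the sentence on histology): the arm difference is "calculated by a non-paired t-test, alternatively a non-parametric test, if the conditions for parametric tests are not present". The threshold follows: "Differences are considered statistically significant if the two-sided p-value is less than 0.05". No multiplicity rule is given.
- **Sizing** (Sample size calculation): "The following sample size determination is based on a non-paired t-test". The SD comes from a source on reduced unstimulated whole flow. The timing is given only as "we are interested in a comparison of change scores (change from baseline to after treatment) between the intervention and placebo group".
- **Visits** (Assessment of salivary flow rate and objective treatment outcome): "At baseline, one and four months after treatment, unstimulated whole saliva will be collected using the spitting method". Four months is tied to histology in the analysis section, never to flow.
- **Measures**: the Discussion counts four flow measurements per visit (whole and submandibular, each unstimulated and stimulated). Secondary outcomes lists them unranked. The assessment section does give a signal: "Changes in the secretion rate of the unstimulated whole saliva in the oral cavity is probably the most important parameter".
- **Baseline range** (Inclusion criteria): "Unstimulated whole saliva flow rate in the range of 0.05-0.20 ml/min".

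**The concern.** Three things are left open in the comparison that justifies the sample size.

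1. Baseline flow is collected but not used as a covariate. The permitted baseline spans a fourfold range and is the denominator of the outcome. A gain of 0.05 ml/min counts as 0.05/0.05 = +100% for a participant who starts at 0.05, and as 0.05/0.20 = +25% for one who starts at 0.20.
2. The visit is not fixed, so there are two candidate results even if unstimulated whole saliva is taken as the measure.
3. That measure has to be inferred from the assessment section and from the source of the SD.

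Safety is the primary outcome, so the trial's main conclusion is not at risk. What is at stake is the efficacy reading, which the Discussion wants to use in designing later trials. The Sample size calculation attaches a Type I error of 0.05 to one test, but the text does not fully say which test that is.

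**Working it through.** **Step 1. Reproduce the plan's figure.** Inputs (Sample size calculation): difference 50%, SD of change 41%, two-sided α 0.05, power 90%.
n per arm = 2(1.960 + 1.282)² × 41² / 50² = 14.1, rounded up to 15. The stated 15 per arm is confirmed. With the exact t distribution, n = 15.16, and power at 15 per arm is 89.7%.

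**Step 2. Implied correlation.** The plan sets the SD of change to 58%/√2 = 41%. Since SD of change = SD × √(2(1−ρ)), this means 2(1−ρ) = 1/2, so ρ = 0.75.

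**Step 3. Analytic effect of baseline adjustment, raw change only.** Residual SD under ANCOVA = 58 × √(1−ρ²). Power uses 15 per arm, difference 50, and 28 df (unadjusted) or 27 df (adjusted). The lower adjusted value allows for estimating the slope (variance × (1 + 1/26)).

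| ρ | SD of change | ANCOVA SD | Power unadjusted | Power adjusted |
|---|---|---|---|---|
| 0.5 (assumed) | 58.0 | 50.2 | 62.5% | 73–75% |
| 0.75 (plan) | 41.0 | 38.4 | 89.7% | 92–93% |
| 0.9 (assumed) | 25.9 | 25.3 | 99.9% | 99.9% |

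This formula does not describe percentage change, so the planned scale has to be simulated.

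**Step 4. Simulation on the plan's scale.** Assumptions: log-normal flow, CV 58%, median 0.10 ml/min, baseline limited to 0.05–0.20, 15 per arm, 20,000 trials per scenario. At ρ = 0.75 the control-arm SD of percentage change is 40.6%, close to the plan's 41%.

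| ρ | True effect | Planned t-test | ANCOVA of % change | ANCOVA of log flow |
|---|---|---|---|---|
| 0.75 | ×1.5 | 80.3% | 80.7% | 83.4% |
| 0.75 | +0.05 ml/min | 88.2% | 91.9% | 95.2% |
| 0.5 | ×1.5 | 52.3% | 55.7% | 61.6% |
| 0.5 | +0.05 ml/min | 61.9% | 69.3% | 80.9% |
| 0.9 | ×1.5 | 99.4% | 99.3% | 99.4% |

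The ×1.5 rows at 0.75 fall below 89.7% because a multiplicative effect also multiplies the treated arm's SD by 1.5. Type I error is 4.6–5.0% for the planned t-test and 4.8–5.1% for percentage-change ANCOVA.

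**Step 5. Near-zero follow-up flows.** The Discussion says that fasting might leave low-flow participants with almost no secretion, but gives no rate. Assume 5% zeros among those with baseline ≤0.10. At ρ = 0.75 and ×1.5, power is 71.5% (t-test) and 70.8% (percentage-change ANCOVA). Log ANCOVA gives 57.7%, 61.2% or 67.4% with a floor of 0.005, 0.01 or 0.02 ml/min. Over 12 scenarios (three correlations, two effects, with and without zeros), percentage-change ANCOVA lies between 1.0 point below and 7.4 points above the t-test.

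**Step 6. Unnamed visit.** The chance of at least one p<0.05 with no effect, using equally correlated change scores and t-tests, is:

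| Correlation between comparisons (assumed) | 0.3 | 0.5 | 0.7 | 0.9 |
|---|---|---|---|---|
| Two visits, one measure | 9.5% | 9.1% | 8.5% | 7.0% |
| Eight comparisons (4 measures × 2 visits) | 30.4% | 25.5% | 19.9% | 12.3% |

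**Step 7. Choice of test.** If the histology test sentence also governs flow, the data choose between the t-test and an unnamed alternative. Taking that alternative as Mann-Whitney, the two disagree on significance in 5–7% of trials at ρ = 0.75 and 11–12% at 0.5. Switching on a normality test gives Type I error of 5.2–5.5%. Always taking the smaller p-value gives 5.6–6.1%.

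**The case against.** The strongest reply is that the lead comparison is already clear enough. The assessment section singles out unstimulated whole saliva and adds that measuring it precisely matters greatly for judging efficacy. The SD comes from the same measure, and the sizing text describes a single test of a single hypothesis. This stands in part: a reader might infer that the plan has no lead measure, and that goes too far. The measure is implied but not designated. The 12–30% figure is therefore only an upper illustration for the case where all eight flow results count equally. The visit remains open in any reading of the running text.

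It can also be said that adjustment buys little. On the percentage scale, for the ×1.5 effect closest to the plan's 50% target, that is right. A reader might take the move from 89.7% to 92–93% as the gain for the planned analysis, but it applies to raw change only.

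Third, keeping percentage change as the outcome does not stop a 0.05 ml/min gain from counting as +100% or +25%. This also stands. ANCOVA on that scale recovers some precision; only a change of scale deals with the unequal weighting.

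Finally, the choice between tests might be read as inflating the error rate materially. Step 7 does not support that.

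**Conclusion.** The point holds as one of precision and prespecification. A reader might infer that unadjusted percentage change biases the comparison or breaks its error rate. It does neither: the trial is randomised, and the single planned test keeps about 5%.

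The firmest part is the unnamed visit, which lets the nominal 5% become 7–10% on the implied lead measure. The gain from baseline adjustment on the percentage scale depends on the correlation:

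- **0.75 (implied by the plan):** about 0.4 points for ×1.5 and 3.5–3.7 points for +0.05 ml/min.
- **0.5 (assumed):** 3–8 points.
- **0.9 (assumed):** none.

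Log-flow ANCOVA gains about 3–7 points at 0.75 when no follow-up flow is zero, and can lose power when some are.

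These sizes rest on the log-normal model, the assumed correlations and the assumed zero rate. Figures 1 and 2 are not shown in the available text, so a visit named there cannot be excluded; the running text names none. The change should be made, but because flow is secondary it does not threaten the trial's main conclusion.

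**What to change.** Before unblinding, add to Statistical analyses:

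1. **Lead comparison.** Unstimulated whole saliva flow at one named visit, for example four months. The other visit and the other three flow measures are supportive.
2. **Model.** ANCOVA with arm and baseline flow. The arm difference, its 95% CI and the p-value all come from that model.
3. **Scale, fixed now.** Percentage change keeps the 50% target and needs no floor for zero follow-ups, but still weights equal absolute gains by baseline. Log flow handles this better and expresses the effect as a ratio of geometric means, but needs a numerical floor, for example 0.02 ml/min (0.02 × 15 minutes = 0.3 g collected).
4. **Test.** No data-driven switch. Report a rank-based ANCOVA as the prespecified sensitivity analysis, and unadjusted percentage change descriptively.
5. **Baseline rule.** Percentage change needs a baseline above zero. The 0.05–0.20 range applies at screening, so if the study baseline is a separate reading, state how a zero would be handled.

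The cost is wording only, with no new data, visits or participants. In some assumed zero-flow scenarios percentage-scale ANCOVA loses up to about 1 point of power against the planned t-test. With zeros and a correlation of 0.9, log ANCOVA loses about 10 points (floor 0.02) or 25–26 (floor 0.005), so the floor must not be left open.

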Salivary gland hypofunction and xerostomia are major complications following radiotherapy for head and neck cancer and may lead to debilitating oral disorders and impaired quality of life. Currently, only symptomatic treatment is available. However, mesenchymal stem cell (MSC) therapy has shown promising results in preclinical studies. Objectives are to assess safety and efficacy in a first-in-man trial on adipose-derived MSC-therapy (ASC) for radiation-induced xerostomia.

Methods

This is a single-center, phase I and II, randomized, placebo-controlled, double-blinded clinical trial. A total of 30 patients are randomized in a 1:1 ratio to receive ultrasound-guided, administered ASC or placebo to the submandibular glands. The primary outcome is safety. The secondary outcomes are efficacy, change in quality of life, qualitative and quantitative measurements of saliva, as well as submandibular gland size, vascularization, fibrosis, and secretory tissue evaluation based on contrast-induced magnetic resonance imaging (MRI) and core-needle-samples. The assessments are performed at baseline (one month prior to treatment), and one and four months following investigational intervention.

Discussion

The trial is the first attempt to evaluate the safety and efficacy of ASCs in patients with radiation-induced xerostomia. The results may provide evidence for the effectiveness of ASC therapy in patients with salivary gland hypofunction and xerostomia and deliver valuable information for the design of subsequent trials.

Trial registration section

EudraCT: 2014-004349-29. Registered: 1st of April 2015

ClinicalTrials.gov Identifier: NCT02513238. First received: 2nd of July, 2015

The trial is prospectively registered.

Key words

Mesenchymal stem cells, xerostomia

Background

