- Morphological changes of the gland tissue, e.g. degree of atrophy, fibrosis, inflammation, and amount of specialized acinic cells including duct/acinic/myoepithelial cell ratio in histological sections from core-needle biopsies taken pre- (baseline) and post-interventional (4 months). An expert head and neck pathologist will be blinded to treatment of participants and evaluate the two sets of biopsies for changes.

Late complications – safety

To detect late complications or late adverse events all study participants, who received ASC-treatment are invited for a check-up one year and three years after treatment. Whether or not participants consent to a late check-up, the Principal Investigator ([name]) will contact participants by telephone to ensure that no subjective complaints have befallen. In case of subjective complaints, participants will be encouraged to meet for a physical examination.

Trial design

Randomized, placebo-controlled, phase I/II trial with double blinding (Figure 1, Figure 2, SPIRIT Checklist (Additional file 1)). All participants will undergo a mini lipo-suction from which ASCs will be ex vivo expanded in a good manufacturing practice (GMP)-approved clean room facility. The Good Clinical Practice committee performs data monitoring, and is independent from the sponsor and has no competing interests.

One month prior to the liposuction, participants will undergo a MRI scan of the submandibular glands, fill-out questionnaires on quality of life and undergo saliva measurements. Also, all patients will have blood samples analyzed for anti-HIV I/II, HBsAg, anti-HBc, anti-HCV and syphilis to fulfil the requirements in the Danish Tissue Act, as well as relevant kidney parameters to secure adequate renal function when using MRI contrast, see below. A core-needle-sample of one of the submandibular glands and a liposuction of the abdomen (approx. 60 ml of adipose tissue) are performed for all participants. Approximately 14 days following liposuction, participants will have ASCs or placebo injected in the submandibular glands on an outpatient basis. Subjects will subsequently undergo a saliva measurement, contrast-induced MRI and fill out questionnaires at baseline, 4 weeks post-intervention and 4 months post-intervention. Finally, at the 4-month visit, a small biopsy is taken from one of the two submandibular glands. The procedure takes place under local anaesthesia. Histology is determined (samples are blinded to the pathologist) (Figure 1).

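### The only significance rule, two-sided p<0.05, has no hierarchy, key efficacy endpoint or exploratory label; read generally, it covers about 22 to 39 non-flow secondary comparisons

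*Combined protocol and SAP*

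**What the plan says.** The Statistical analyses section compares percentage change in salivary flow between arms. It then turns to gland histology and states: "The differences between the intervention and the placebo group will be calculated by a non-paired t-test, alternatively a non-parametric test". The sentence that follows is the only significance rule in the documents: "Differences are considered statistically significant if the two-sided p-value is less than 0.05". No adjustment, testing order or restriction goes with it.

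The Sample size calculation section concerns flow alone. Its stated error rate belongs to that one comparison: "The Type I error probability associated with this test of this null hypothesis is 0.05".

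The secondary outcomes are much wider than flow. The chemical analysis covers pH, bicarbonate and "sodium, potassium, calcium, phosphate, chloride and fluoride [16], total protein, selected proteins [31] and amylase [32"]. Histology covers "degree of atrophy, fibrosis, inflammation, and amount of specialized acinic cells including duct/acinic/myoepithelial cell ratio". There are also a patient-rated and a physician-rated xerostomia measure, three MRI measures (volume, fibrosis, vascularisation) and, in the abstract, change in quality of life. Saliva, questionnaires and MRI are repeated at about one and four months after the intervention; the second biopsy is taken at four months only.

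On purpose, the abstract says: "The results may provide evidence for the effectiveness of ASC therapy in patients with salivary gland hypofunction and xerostomia". The Discussion lists efficacy among the things the trial sets out to establish, and also leaves its verification to later trials.

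**The concern.** The primary outcome is safety, so every statement about efficacy will rest on secondary outcomes. The plan does not say which of them carries the efficacy question, at which visit, or that the rest are exploratory. A rule that calls any difference below 0.05 significant then lets whichever measure crosses the line be reported as an effect of ASC.

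Small arms make this worse. With 15 per arm, an unpaired t-test reaches p<0.05 only when the observed difference is at least 2.048 × √(2/15) ≈ 0.75 SD. A chance finding will therefore look large, and since the trial is meant to inform the design of later trials, it could shape the choice of endpoint or the assumed effect there.

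**Working it through.** **The plan's own figure.** Inputs from the Sample size calculation: difference 50%, SD of the change score 41% (58%/√2), two-sided α 0.05, power 90%. n per arm = 2 × [41 × (1.960 + 1.282)/50]² = 14.13, rounded up to 15. This reproduces the plan's 15 per arm; the exact t-test power at 15 per arm is 89.7%. The calculation covers one flow comparison and leaves the other outcomes aside.

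**Counting the non-flow comparisons.**

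| Family | Measures | 4 months only | Both visits |
|---|---|---|---|
| Saliva composition (the unspecified selected proteins counted once) | 11 | 11 | 22 |
| Xerostomia (patient VAS, physician rating) | 2 | 2 | 4 |
| Quality of life (assumed to be one separate score) | 1 | 1 | 2 |
| MRI | 3 | 3 | 6 |
| Histology (five features assumed, 4 months only) | 5 | 5 | 5 |
| Total | 22 | 22 | 39 |

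Without a separate quality-of-life score, the totals are 21 and 37. If composition is tested in both the unstimulated and the stimulated swab collection, 39 becomes 39 + 22 = 61. Flow itself (four measures × two visits = 8) is left out of these totals.

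**Expected false positives if ASC has no effect.** This is the number of tests × 0.05, and it holds for any correlation because expectations add: 22 × 0.05 = 1.1; 39 × 0.05 = 1.95; 61 × 0.05 = 3.05.

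**Chance of at least one, either direction, independent tests.** 1 − 0.95^22 = 67.6%; 1 − 0.95^39 = 86.5%; 1 − 0.95^61 = 95.6%.

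**Chance of at least one favouring ASC, independent tests.** 1 − 0.975^22 = 42.7%; 1 − 0.975^39 = 62.7%.

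**With correlated outcomes.** The documents give no correlations, so an equal correlation ρ between outcomes is assumed. The figures come from 40,000 simulated null trials with 15 per arm and unpaired t-tests:

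| ρ | 22 tests, either direction | 39 tests, either direction | 39 tests, favouring ASC |
|---|---|---|---|
| 0.3 | 57.5% | 74.6% | 40.6% |
| 0.5 | 44.9% | 57.4% | 29.1% |
| 0.7 | 31.0% | 38.5% | 19.4% |

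**Why not a blanket correction.** Bonferroni over 39 tests gives α = 0.05/39 = 0.00128. If the 50% flow difference were tested at that level, power at 15 per arm would fall from 89.7% to about 43%, and 90% power would need about 28 per arm by the normal approximation.

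**The case against.** The strongest reply concerns the reach of the rule. The t-test sentence sits in the histology paragraph, the section names only flow and histology, and no test is named for composition, MRI, VAS or quality of life. On that view the plan is unclear and not committed to dozens of tests. This stands as far as it goes: applying the rule to every measure is a reading of the text. But on the narrow reading the other families have no rule at all, and the same clarification is needed.

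The second reply is that this is a 30-patient phase I/II trial with a safety primary outcome. The 0.05 error is tied to the flow test, unstimulated whole saliva is described as the leading parameter for efficacy, and verification is left to later trials. That limits the seriousness, since no primary conclusion is inflated. It does not supply what is missing: the leading parameter is never made a key endpoint or tied to a visit, and nothing is labelled exploratory.

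Third, a reader might infer that there are at least 39 comparisons and that a chance benefit of ASC is close to certain. The documents support neither. The count of 39 needs separate tests at both visits, a distinct quality-of-life score and five histology tests, none of which is stated; the histology list is introduced as examples. The 86% assumes independence, although the same measure recurs at two visits and bicarbonate is estimated from the ionic balance. It also counts differences in favour of placebo.

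**Conclusion.** The concern holds as a gap in the inference rule, of moderate size. Applied generally, the rule covers roughly 22 to 39 non-flow comparisons, and up to 61 on the widest reading. The firmest figure is the expected number of false positives under no effect, 1.1 to 1.95 for 22 to 39 tests, because it does not depend on correlation. The chance of at least one depends on the assumed correlation but is well above 5% in every case tried. The chance of one favouring ASC is smaller; those figures assume that each measure has a direction that counts as benefit.

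The conclusion rests on reading the significance sentence as general and on the counting assumptions shown. The safety outcome and the sample size are untouched. That a chance finding would in fact be presented as a treatment effect is a risk the plan leaves open; the documents do not show that it would happen.

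**What to change.** Amend the Statistical analyses section before unblinding:

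- Limit the term statistically significant to one comparison: the between-arm difference in change in unstimulated whole saliva flow rate, at one post-treatment visit named in advance. This is the measure whose variability underlies the sample size. The sponsor has to choose the visit, because the plan does not.
- Report every other secondary outcome as a between-arm difference with a 95% CI, labelled exploratory, with no claim of significance. This covers the other flow measures and visits, composition, VAS, physician rating, quality of life, MRI and histology.

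This is a cheap improvement. It takes a short change to the text and one decision on the visit. The single test keeps its 0.05 error, and the 15 per arm and the planned power stay as they are. The cost is that fewer secondary results can be called significant.
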